We will undertake a prospective, interventional, non-randomised, implementation study of mPOCT for COVID-19 in adults presenting to University Hospital Southampton NHS Foundation Trust. A brief validation and training phase will be followed by the post-implementation phase where patients will be recruited and tested at the point-of-care using the QIAstat-Dx Respiratory SARS-CoV-2 Panel. We will initially test patients suspected of COVID-19 based on current PHE case definitions and then progress to testing all patients with ARI as the outbreak becomes more widespread in the UK and the risks of admitting patients to hospital with unsuspected COVID-19 are high. Clinical and infection

control teams will be informed of these results in real time. The control group will consist of patients who were tested for SARS-CoV-2 by laboratory PCR but not recruited to the study during the same time period. This allows us to have a comparable control group as the outbreak progresses and hospital pathways change, as opposed to a pre-implementation group which predominantly is expected to consist of community-based patients tested in hospital for containment reasons. Only anonymised, routinely collected hospital data will be obtained for the control group. Outcome measures will be by assessed by retrospective case note analysis and will include: time to result, time in isolation facilities, detection of COVID-19 cases not initially suspected (based on current PHE case definition), antibiotic use, antiviral use, length of hospital stay, ward closures and hospital resource use. Multivariate analysis will be used to control for the effect of confounding variables between the groups.

Potential benefits to patients and the NHS

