1. To assess the clinical impact of mPOCT for respiratory viruses including SARS-CoV-2 on outcomes measures including: time to test result, time in COVID-19 assessment cohort areas, time to definite ward move, length of stay in hospital, use of antibiotics, use of antivirals, ward closures, and hospital resource use, in adults hospitalised with ARI.

2. To assess the implementation feasibility of mPOCT for COVID-19.

3. To assess the ease-of-use, reliability and real-world diagnostic accuracy of the QIAstat-Dx SARS-2-CoV assay, , using respiratory samples prospectively collected from adults presenting to hospital with ARI, compared to the reference standard of PHE laboratory RT-PCR for SARS-CoV-2.

6. Recruitment and Study Processes

Overview

This is a non-randomised, controlled, implementation study of mPOCT for respiratory viruses including COVID-19 with prospective recruitment for participants in the intervention phase. The intervention consists of testing respiratory samples from patients at the point-of-care using the QIAstat-Dx Respiratory SARS-CoV-2 Panel. In the contemporaneous control group, routinely collected data on outcomes in patients tested for COVID-19 using laboratory RT-PCR, including time to test result. In the intervention phase patients will be tested using the QIAstat-Dx Respiratory SARS-CoV-2 Panel with results delivered immediately to the clinical and infection control team and outcome and diagnostic accuracy data collected retrospectively. A brief validation phase will precede the intervention phase. Study processes that patient-participants undergo in intervention phase are summarised in Figure 1.

[figure not shown]

Figure 1: Participant flow through the study

POCT = point-of care test

*if lacks capacity to consent, participant's consultee may be substituted here

Control group

Patients (≥18 years old) presenting to hospital with ARI who have been tested for SARS-CoV-2 during the same time period as part of standard clinical care (but not included in the intervention) via University Hospital Southampton NHS Foundation Trust (UHS) will be identified via (laboratory) information management system and select clinical data will be obtained by electronic records including age, sex, co-morbidity, observations, blood test results, length of hospital stay, and time to test result. Consent is not obtained for these patients, and only anonymised data already collected as part of routine clinical care will be used.

Screening

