Non-hospitalised hospital staff members may be included in the intervention phase of the study, if they satisfy the other inclusion & exclusion criteria. The same consent and study procedure processes are followed. However, their results will not be included in analyses of most outcome measures, with the exception of time to result. Days away from work may be used as an additional outcome measure.

Participant Withdrawal

A participant, or their consultee where a participant lacks capacity, may decide to withdraw from the study at any time, without giving reason, and with no detriment to their medical care or legal rights.

The chief investigator may withdraw a patient from the study in the interests of participant safety or the integrity of the research study, or on the advice of the sponsor's representative (R&D department).

Any patient, or their consultee where a patient lacks capacity, who is withdrawing from the study has the options withdraw and have data and/or samples collected so far retained, or withdraw and have their data and/or samples destroyed (but signed consultee declaration forms, minimal personal identifiable information to record the withdrawal, and any completed point-of-care test result will be retained). Although the study procedures are very brief, if a patient loses capacity after enrolment but before the study procedures are completed, consultee consent must be sought to continue with any study procedures, or the participant must be withdrawn.

A note to file would normally be sufficient to record any withdrawal.

7. Outcomes

Primary outcome

• The primary outcome measure is the time from COVID-19 test being requested to the result being available to clinical teams.

Secondary Outcomes

- The time from presentation to hospital to COVID-19 test result
- Time spent in COVID-19 assessment cohort area
- Time to definitive ward move
- Number of bed moves •
- Duration of hospitalisation •
- Number and proportion of clinically unsuspected COVID-19 positive patients detected •
- Proportion of patients treated with antibiotics
- Proportion of patients treated with single doses or brief courses (<48 hours) of antibiotics •
- Duration of antibiotic use, days
- Proportion of all influenza antiviral use occurring in influenza positive patients •
- Proportion of all influenza antiviral use occurring in influenza negative patients •
- Time from admission to influenza antiviral commencement

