Accepting that the prevalence of COVID-19 during the study is highly speculative at present, and so formal samples size calculation for diagnostic accuracy studies are not possible, testing 500 patients will allow us to make an ongoing assessment of the real-world diagnostic accuracy of the QIAstat-Dx Respiratory SARS-CoV-2assay compared to the current reference standard of laboratory PCR testing using the PHE RdRP assay.

The control group will be 500 patients for an adequate comparison.

9. Data collection

Demographic and clinical data will be collected for all patients at enrolment including: age, sex, ethnicity, smoking status, vaccination status, co-morbidities, medication use, symptoms, duration of illness prior to hospitalisation, observations (pulse rate, respiratory rate, blood pressure, oxygenation status), laboratory results, radiology results, antimicrobial and antiviral use prior to hospitalisation and provisional diagnosis. Data will be recorded on a Case Report Form, which we intend to be electronic (ALEA). Once patients have been discharged or after 30 days (whichever is soonest), clinical data will be collected retrospectively from electronic and physical case notes including: use of antivirals, duration of antivirals, time from assessment to antiviral use, use of side room facilities, time from assessment to isolation facility use, time to clinical stability, duration of supplementary oxygen use, duration of hospitalisation, complications including ICU and RHDU admission, representation and readmission to hospital within 30 days, final diagnosis and mortality. The number of diagnostic tests and procedures performed will also be recorded and data will also be collected on the turnaround time of respiratory virus test results in each group.

10. Data Management

The subjects' anonymity will be maintained. The study team will keep a log of each subject's name, hospital ID number, date of birth, and unique participant trial number. The participant details will be recorded on the secure NHS Edge system in a similar manner, including NHS number. This participant trial number is used on documents after screening to maintain confidentiality. Documents that are not anonymous (e.g. signed informed consent forms) will be maintained separately, in strict confidence.

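### The protocol does not commit to one record source for both groups, so secondary outcomes that rest on record review may be detected differently in participants and controls

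*Protocol*

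**What the plan says.** Three parts of the protocol describe where outcome data come from.

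- **Section 9 (Data collection)** opens with "Demographic and clinical data will be collected for all patients at enrolment", recorded on a Case Report Form. It then says that, after discharge or 30 days, "clinical data will be collected retrospectively from electronic and physical case notes". The follow-up items include antiviral use, its duration and start time, side-room use, time to isolation, duration of hospitalisation, ICU or RHDU admission, readmission and mortality. The section ends by saying that "data will also be collected on the turnaround time of respiratory virus test results in each group".
- **Section 6 (Control group)** says that for controls "select clinical data will be obtained by electronic records including age, sex, co-morbidity, observations, blood test results, length of hospital stay, and time to test" (the last item being how long the result took). It adds: "Consent is not obtained for these patients, and only anonymised data already collected as part of routine clinical care will be used".
- **Section 2 (Overview, Methods)** says "Only anonymised, routinely collected hospital data will be obtained for the control group", and in the next sentence "Outcome measures will be by assessed by retrospective case note analysis", with no distinction between groups.

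Section 7 lists the secondary outcomes. They include number of bed moves, time in the assessment cohort area, time to definitive ward move, several antiviral measures, and antibiotic measures such as "Proportion of patients treated with single doses or brief courses (<48 hours) of antibiotics".

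**The concern.** In a non-randomised comparison with no blinding described, the outcome has to be found in the same way in each group. If staff search electronic and paper notes for one group and only selected electronic records for the other, an event recorded only on paper is counted in the first group and missed in the second. The difference then reflects the search and not the test.

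Outcomes that turn on a single record are the most exposed: one antibiotic dose, a brief course, or the start time of an antiviral. The bias need not run one way. If controls were under-captured, any-antibiotic use would look lower in controls, which counts against point-of-care testing. Missed brief courses would make early stopping look more common with point-of-care testing, which counts in its favour.

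Objective 1 in Section 5 rests largely on outcomes of this kind, so the protocol should settle the source before data are extracted.

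**Working it through.** The protocol gives no figure on this point to reproduce. The check sets the texts side by side and then tests how sensitive a comparison would be.

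**Step 1. Sources by section**

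| Section | Group named | Source |
|---|---|---|
| 2, Methods | Controls | Anonymised routine hospital data; electronic or paper not specified |
| 2, Methods, next sentence | None | Retrospective case note analysis |
| 6, Control group | Controls | Selected data from electronic records |
| 9 | None; framed by enrolment and the Case Report Form | Electronic and physical notes |
| 9, last sentence | Both groups | Turnaround time only |

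Controls are never enrolled, so Section 9 most naturally describes participants. The overview of Section 6 also treats the groups separately: routinely collected outcome data for controls, retrospectively collected outcome data in the intervention phase. If Section 9 covers participants only, the sources differ by group. If Sections 2 and 9 cover both groups, they conflict with the electronic route in Section 6. Either way the text needs reconciling.

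**Step 2. Which outcomes are exposed**

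- Time to result: listed for controls in Section 6 and collected in each group under Section 9. Not affected.
- Length of stay: named in both lists, so a control source exists.
- Antiviral use, duration and start time: in the Section 9 list, not named in the control list. Exposed.
- In-hospital antibiotics, bed moves, cohort-area time, definitive ward move: in neither list. Source unstated, so possibly exposed.

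Both lists are introduced as examples, so absence from a list does not show that an item will not be collected.

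**Step 3. Would the planned analysis repair it?** Section 11 adjusts for confounders. That addresses differences in patients, not differences in finding events. Section 11 also considers multiple imputation if missing data exceed 5%. A dose absent from the source searched is likely to be coded as not given rather than missing, so that trigger may never be reached.

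**Step 4. Illustration on assumed values.** From the protocol: 500 per group and a chi-square test for binary outcomes. Assumed: true antibiotic use of 80% in both groups, the capture rates below, and two-sided alpha of 0.05.

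With 98% capture in participants, observed use is 0.80 × 0.98 = 0.784.

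- Control capture 90%: 0.80 × 0.90 = 0.720. Difference 0.064; pooled proportion 0.752; SE = √(0.752 × 0.248 × 2/500) = 0.0273; z = 2.34; p about 0.02.
- Control capture 95%: 0.80 × 0.95 = 0.760. Difference 0.024; pooled proportion 0.772; SE = √(0.772 × 0.228 × 2/500) = 0.0265; z = 0.90; p about 0.37.

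With full capture in participants, the chance of a significant result in the direction of the bias is Φ[(d − 1.96·SE₀)/SE₁], where SE₀ is the pooled and SE₁ the unpooled standard error. For 0.80 against 0.76: SE₀ = √(2 × 0.78 × 0.22/500) = 0.0262; SE₁ = √[(0.80 × 0.20 + 0.76 × 0.24)/500] = 0.0262; (0.04 − 0.0514)/0.0262 = −0.43; Φ = 0.33.

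| True use, both groups | Control capture 98% | 95% | 90% |
|---|---|---|---|
| 50% | 5% | 12% | 35% |
| 70% | 7% | 22% | 65% |
| 80% | 9% | 33% | 84% |
| 90% | 15% | 58% | 98% |

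These count one tail only, where the nominal rate is 2.5%. With equal capture in both groups there is no such excess. The table shows sensitivity to unequal capture; it does not estimate the bias in this trial.

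**The case against.** A reader might infer that the protocol has paper notes searched for tested participants and only electronic records for controls, and that the antibiotic, bed-move and ward-time comparisons are therefore biased. The documents do not support that.

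- The Section 9 sentence names no group, and the section opens by referring to all patients.
- Section 2 mentions case note analysis directly after describing the control data, and can be read as covering both groups. It restricts controls to routine hospital data, which could include paper; only Section 6 says electronic.
- The control list in Section 6 is not exhaustive.
- In-hospital antibiotics, bed moves and ward times appear in neither source list, so no source difference is documented for them.
- No section says which items this hospital holds only on paper. An item held fully in electronic form carries no source bias.
- The capture rates above are assumed, and the 95% case compared with 98% is far from significant.

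It can also be said that extraction sheets belong in a data management plan or a separate SAP.

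All of this stands against the stronger reading. It does not remove the narrower point. The protocol itself states the sources, states them inconsistently, and nowhere promises a common procedure. A later operational document would have to depart from one of these sections in order to follow another.

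**Conclusion.** The point holds as an inconsistency with a possible consequence, not as a demonstrated bias. Sections 2, 6 and 9 leave open whether controls' physical notes are reviewed, and none commits to the same source for both groups. If the sources do differ, secondary outcomes found by record review can be detected differently by group, and neither the confounder adjustment nor the imputation rule would correct it.

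Size and direction are unknown. The effect could be nil if all items are electronic. On the assumed values, a shortfall of a few points in control capture gives anything from a negligible difference to one that a chi-square test with 500 per group would often call significant. The primary outcome, as defined in Section 7 (request to result), is unaffected. Section 11 names isolation-facility use as primary, which is a separate discrepancy.

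The change is worth making because it is specific and cheap, not because harm has been shown.

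**What to change.** Reconcile Sections 2, 6 and 9. State in Section 9 that each outcome and covariate compared between groups is extracted for both groups from the same source, namely the electronic records available for controls, with the same definitions and look-back window. Extend the control data items in Section 6 to match the Section 7 outcomes, including antibiotics, antivirals, bed moves and ward times where these are held electronically.

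Use physical-note data only to describe the intervention group or in a sensitivity analysis. Before giving up any comparison, check whether an equivalent electronic source exists for controls. Only where none exists should the outcome be reported descriptively, without a between-group test.

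The cost is protocol and data-sheet wording, plus a check of which items are held electronically; no additional patients are needed. The downside is that some paper-only detail on participants is left out of the comparisons, and an outcome with no equivalent control source loses its formal test.

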We hypothesise that the use of a routine mPOCT for respiratory viruses including SARS-CoV-2 in adults presenting to hospital with suspected COVID-19 and/or ARI will dramatically reduce the time from patient presentation to results, compared to the current standard of PHE laboratory RT-PCR. We expect that timely detection or exclusion of COVID-19 will lead to improvements in early directed isolation facility and enhanced PPE use or de-isolation/de-escalation, in addition to other potential benefits such as reduced length of stay, improved use of antibiotics and antivirals and resource use and cost for the NHS. The detection of COVID-19 positive cases presenting to hospital and not initially suspected based on current the PHE case definition will prevent widespread nosocomial transmission of SARS-CoV-2 and associated hospital ward closures.

3. Abbreviations and Definitions

AE: Adverse Event AMU: Acute medical unit ARI: Acute respiratory illness CES: School of Clinical and Experimental Sciences, Faculty of Medicine University of Southampton **CI:** Chief Investigator COVID-19: Coronavirus disease 2019 CRF: Case Report Form ED: Emergency Department GICU: General Intensive Care Unit HRA: Health Research Agency ICU: Intensive care unit mPOCT: Molecular Point-of-Care test PCR: Polymerase Chain Reaction PHE: Public Health England PI: Principal Investigator POCT: Point-of-Care Test **PPE: Personal Protective Equipment REC: Regional Ethics Committee** RHDU: Respiratory High Dependency Unit RT-PCR: Reverse Transcriptase Polymerase Chain Reaction SAE: Serious Adverse Event

SARS-CoV-2: Severe acute respiratory syndrome coronavirus 2

UHS: University Hospital Southampton NHS Foundation Trust

WHO: World Health Organisation

4. Introduction

COVID-19

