Our previous randomised controlled trials have demonstrated that routine syndromic mPOCT for respiratory viruses leads to the generation of accurate, actionable results in under 2 hours compared with 1-2 days for laboratory testing. Physicians act on these results and mPOCT is associated with a number of clinical benefits including reduced antibiotic use and length of stay [6]. Further analysis shows that a very rapid turnaround time is critical to achieving these improvements and the best outcomes were associated with the quickest results [7], definitively showing that testing for respiratory viruses should take place at the point-of-care rather than in centralised laboratories. In our most recent trial (FluPOC) routine mPOCT for influenza was associated with vast improvements in the detection of influenza and the timely and appropriate use of isolation facilities and antivirals [8] and was also associated with improvements in clinical outcome.

Using syndromic mPOCT to detect COVID-19

The current situation of an emerging pandemic of a novel coronavirus is ideal for using a syndromic mPOCT approach including testing for COVID-19. COVID-19 is clinically indistinguishable from illness caused by other respiratory viruses and so testing syndromically with a single test is clinically desirable and efficient. Accurate testing for COVID-19 at the point-of-care will enable the generation of results in near real-time, allowing early appropriate and directed use of enhanced isolation facilities for patients and PPE for staff, for SARS-CoV-2 infected patients and rapid de-isolation for those testing negative. Testing for influenza and other respiratory viruses at the same time enables early identification of other important pathogens simultaneously and without the need for duplicate testing or for processing of additional samples in biological safety level 3 (BSL3) facilities.

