Summaries of all baseline characteristics will be presented using means and standard deviations, medians and interquartile ranges, or frequencies and percentages, as appropriate. The groups will be compared using chi-square tests for equality of proportions for binary data (e.g. proportion of cases of influenza detected) and using independent-samples t-tests or non-parametric equivalent as appropriate for continuous data (e.g. duration of isolation facility use, etc.).

The primary outcome measure (median duration of isolation facility use) will be compared between the groups using the Mann-Whitney U test. Multivariate analysis will be performed to adjust for confounding variable in view of the non-randomised nature of the study.

12. Safety

Serious Adverse Events

The risks of respiratory tract sampling and additional blood tests being taken are minimal and where occurring are likely to be mild. No additional adverse events related to mPOCT for respiratory viruses including COVID-19 are anticipated. However active monitoring and reporting of severe adverse events will be undertaken. A Serious Adverse Event (SAE) is any adverse event that:

- Results in death

- Is life-threatening

- Requires hospitalisation or prolongation of existing hospitalisation

- Results in persistent or significant disability or incapacity
- Consists of a congenital anomaly or birth defect

In the event of a SAE, a study doctor will consider the likelihood of the event being related to the study based on the documented evidence from the treating clinicians. SAEs will be reported via the sponsor's standard forms and processes. SAEs will be reported within 24 hours of the study team learning of the SAE. In the event of a SAE, the PI will be involved in deciding whether this was a study-related event. In the event of a study-related SAE, the REC will be informed as per HRA regulations.

Participants already admitted to AMU, or another hospital ward including high dependency or an intensive care unit, or are in ED but with a decision already made to admit, are considered already hospitalised. However, an adverse event leading to prolongation of their existing hospitalisation will be counted as an SAE.

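### Isolation duration is compared in one unadjusted test pooled over SARS-CoV-2 positive and negative patients, so a difference in case mix between the non-randomised groups can create or hide a result

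*Protocol*

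**What the plan says.** Section 11 (Statistical Analysis Plan) fixes the test: "The primary outcome measure (median duration of isolation facility use) will be compared between the groups using the Mann-Whitney U test". It also gives duration of isolation facility use as its example of a continuous variable. It does not separate patients by SARS-CoV-2 result. The next sentence adds: "Multivariate analysis will be performed to adjust for confounding variable in view of the non-randomised nature of the study". No covariates are named.

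The Methods part of Section 2 lists isolation time among the outcome measures: "time to result, time in isolation facilities, detection of COVID-19 cases not initially suspected". The hypothesis in Section 2 is that timely detection or exclusion of infection "will lead to improvements in early directed isolation facility and enhanced PPE use or de-isolation/de-escalation". Section 4 (Using syndromic mPOCT to detect COVID-19) ties each part to a result: early directed isolation "for SARS-CoV-2 infected patients and rapid de-isolation for those testing negative".

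Section 7 names a different primary outcome: "The primary outcome measure is the time from COVID-19 test being requested to the result being available to clinical teams". Isolation duration is not in the Section 7 list. Section 9 does collect "use of side room facilities, time from assessment to isolation facility use".

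**The concern.** The benefit sought is not the same quantity in the two kinds of patient. In a negative patient the gain is a shorter time in isolation. In a positive patient it is an earlier start, and the total time says little about that. A pooled duration mixes short times from negatives with long times from positives, weighted by each group's positive fraction.

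Nothing in the design makes those fractions equal. Section 6 has all patients with acute respiratory illness approached for the intervention. Controls are patients tested in routine care over the same period and not recruited. Section 8 declines to predict prevalence.

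A shorter pooled duration with point-of-care testing could therefore mean faster release of negatives, fewer positives, or positives isolated late. Only the first is a benefit. A real gain in negatives could also be hidden if the intervention group holds more positives.

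**Working it through.** The protocol has no calculation to reproduce. It gives 500 per group, chosen by kit supply, and no alpha, effect size or spread for isolation time.

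**Assumptions (not in the protocol).** Two-sided 5%. Lognormal isolation times: positives median 144 h, log-SD 0.7; negatives median 36 h (or 72 h), log-SD 0.6. Positive fractions are varied.

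**1. Case mix alone, no effect of testing within either result.** Let θ be the probability that a random positive has a longer isolation time than a random negative, and p₁ and p₀ the positive fractions in the intervention and control groups. Writing out the four positive/negative pairings gives

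P(intervention time > control time) = 0.5 + (p₁ − p₀)(θ − 0.5).

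The Mann-Whitney test has its nominal error only if this equals 0.5, that is, if p₁ = p₀.

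- Negatives 36 h: θ = Φ(ln(144/36)/√(0.49 + 0.36)) = Φ(1.386/0.922) = 0.934.
- Negatives 72 h: θ = Φ(0.693/0.922) = 0.774.
- Null standard error with 500 v 500: √(1001/(12 × 500 × 500)) = 0.0183.

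For a 10-point difference:

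- 36 h: shift 0.10 × 0.434 = 0.0434, z = 2.37, rejection ≈ Φ(2.37 − 1.96) = 66%.
- 72 h: shift 0.10 × 0.274 = 0.0274, z = 1.50, rejection ≈ Φ(1.50 − 1.96) = 32%.

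Simulation (2,000 trials per row) agrees. The adjusted column is a regression of log duration on group and SARS-CoV-2 status, without interaction.

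| Positive, intervention v control | Negatives' median | Pooled test | Negatives only | Adjusted for status |
|---|---|---|---|---|
| 40% v 40% | 36 h | 5% | 5% | 5% |
| 35% v 40% | 36 h | 23% | 4% | 4% |
| 35% v 45% | 36 h | 67% | 6% | 5% |
| 10% v 20% | 36 h | 68% | 5% | 5% |
| 10% v 20% | 72 h | 32% | 5% | 5% |

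A second model (medians 2 and 7 days, log-SD 0.8) gives 50% pooled rejection at 35% v 25% and 52% at 20% v 10%.

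**2. A modest true effect.** Negatives go from 36 to 24 h, and positives gain 24 h (144 to 168 h).

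| Positive, intervention v control | Pooled power | Negatives only | Adjusted for status |
|---|---|---|---|
| 20% v 20% | 100% | 100% | 100% |
| 40% v 40% | 92% | 100% | 99% |
| 50% v 50% | 49% | 100% | 86% |
| 60% v 60% | 11% | 100% | 38% |
| 50% v 40% | 5% | 100% | 96% |

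The loss does not need any lengthening in positives. With positives unchanged at 144 h, pooled power is 99% at 40% v 40% and 21% at 50% v 40%. In the second model, with negatives going from 2 to 1.6 days and positives unchanged, pooled power falls from 74% at equal 30% to 7% at 35% v 25%. At 45% v 25%, 49% of trials reject in the wrong direction.

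**3. A large true effect.** Negatives go from 72 to 24 h, and positives gain 24 h. Pooled power is 100% at 20% v 20%, 40% v 40%, 50% v 50% and 50% v 40%, and 99% at 60% v 60%.

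**The case against.** **The protocol already promises adjustment.** Unequal positivity is ordinary confounding, and adjusting for SARS-CoV-2 status restores about 5% error and 96% power at 50% v 40%. This largely stands. A protocol may also leave the covariate list to the statistical analysis plan, so its absence is no fault. But the test that Section 11 fixes for isolation duration is the unadjusted one. A single adjusted effect would also still average two different effects, as the 38% at equal 60% positivity shows.

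**Opposite directions are not a stated hypothesis.** A reader might infer that point-of-care testing is meant to lengthen isolation in positives, so that two benefits cancel. The documents do not say so. They speak of earlier, directed isolation. The account of routine diagnosis in Section 4 has suspected cases isolated until the result arrives, so suspected positives are isolated in either group. Longer total isolation is implied mainly for positives who were not clinically suspected. The extra 24 h given to every positive above is an assumption.

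**The effect may be large.** Section 4 puts the central laboratory's sampling-to-result time at around 3–4 days, against about 1 hour for the new test, and expects most suspected patients to be negative early in the outbreak. There the pooled test keeps its power. This stands for power, although regional turnaround is not given. It does not protect against false rejection, since 10% v 20% is also low positivity.

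**Isolation duration may not survive as an outcome.** Section 7 omits it and names another primary outcome. That contradiction needs its own reconciliation. The present point applies only where isolation duration is kept.

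**Overall isolation use is a fair resource question.** It is, and the pooled figure can serve it as a description.

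**Conclusion.** The point holds in a limited form. The stated test is pooled and unadjusted, the groups are not randomised, and the benefit differs by test result, so the comparison can reflect case mix. Under the assumed times, a 10-point difference in positivity gives about 65–70% rejection with no effect (about 30% at 10% v 20% with negatives at 72 h), against about 5% within negatives. These sizes rest wholly on assumed durations and positivity.

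A reader might go further and conclude that the trial cannot answer its isolation question. The documents do not support that. Adjustment that included SARS-CoV-2 status would remove most of the false rejection, and the loss of power is confined to modest effects with high or unequal positivity.

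**What to change.** First reconcile Section 11 with Section 7 on the primary outcome. Then, wherever isolation duration is kept, replace the pooled test in Section 11 with two main comparisons by SARS-CoV-2 result at presentation:

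- in negatives, duration of isolation facility use;
- in positives, time from assessment to isolation facility use.

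Apply the confounder adjustment within each. Keep the pooled duration as a descriptive summary of resource use, with each group's positive fraction beside it.

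The cost is wording. Every patient is tested, and side room use and time to isolation are already on the Section 9 list. The same items must be read from the records for controls, but any comparison of isolation duration needs the start time anyway. Laboratory PCR, which is both the routine test in controls and the accuracy reference in Section 5, could classify both groups in the same way. The downside is two smaller comparisons instead of one, with the one in positives imprecise if few are positive.
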